4 STUDY DESIGN

4.1 General Design

This study is a prospective, single-center healthy volunteer validation study.

[REDACTED]

If the volunteer decides to participate in this study, informed consent is explained and a copy is handed over or sent by email and a date is set for the screening visit, and for the hypoxia procedure study session, which will be at least 24 hours after obtaining informed consent. A screening blood and urine test will be performed as well as physical examination and ECG recording. All inclusion criteria and exclusion criteria needs to be confirmed before a volunteer is eligible for the study and can be assigned a study number. For women, a negative pregnancy test must be confirmed before the onset of study session.

To derive a representative population sample size, volunteer inclusion will be stratified to skin pigmentation, and at least 4 subjects should have a dark skin pigmentation. Skin pigmentation will be assessed using the Massey Scale[10].

The names and study numbers of those who sign a consent form will be recorded in an enrollment form stored in a password protected electronic file. Demographic data (ASA physical status classification, age, gender, weight, height, skin pigmentation, co-morbidity, and regular medication history) will be recorded in a case report form (CRF) kept separate from any subject identifiable data. After IRB/ethics committee approval for the study and written informed consent of each volunteer, the volunteers will undergo the study session. The study will take place in a controlled environment at

[REDACTED]

UMCG, under supervision of at least one qualified anesthesiologist.

[REDACTED]

We aim to include 25 subjects in the study, and withdrawn subjects will be replaced by another volunteer. Therefore, several extra subjects are recruited to account for withdrawn subjects and screen-failures. Subjects who did not complete the study procedures due to errors of technical nature and who did not meet any of the stopping criteria during the procedure, can be asked to repeat the study procedures.

[REDACTED]

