5.3 Treatment of Subjects

Each subject will undergo the following interventions in a standardized sequence:

- Stepped Hypoxia Plateau Sequence Protocol by changing inspiratory oxygen fraction (FiO₂):
 - Normoxia: room air (FiO₂ 0.21) (baseline)
 - Hypoxia [REDACTED]
[REDACTED]
[REDACTED]
- After measurements have been completed, the subject will be allowed to breathe room air.
[REDACTED] oxygen saturation (SaO₂ or SvO₂, respectively) will be measured by drawing blood samples [REDACTED]

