5.4 Study Procedures

- O3 rSO₂ sensors will be applied before each study session.
- All subjects will have their medical history done at the time of the screening period. Female subjects will have a pregnancy test prior to being admitted to the study.
- Upon passing the screening tests, each subject will read and sign an Informed Consent to Act as a Human Research Subject form prior to being enrolled in the study.

- A (20G) radial artery catheter will be inserted in the radial artery of the non-dominant hand. It will be inserted under local anesthesia (Lidocaine), only after the Allen Test is negative. The arterial catheter will be used for SaO_2 measurements and for continuous monitoring of arterial blood pressure.

- The venous sheath and radial artery will be continuously flushed with NaCl 0.9% by a pressure infusion bag (per institutional policy).

- The Masimo O3 regional oximeter rSO₂ sensor will be placed on the skin [REDACTED]
[REDACTED]
The rSO₂ sensors may be placed on the forehead as well.

The rSO₂ sensors may be placed on the forehead as well.

- The face-mask will be applied to the subject and it will be connected to the breathing circuit. Note, the subject will still breathe room air at this moment.

- Hypoxia Plateau Sequence Protocol by changing inspiratory oxygen fraction (FiO_2):

After all catheters and sensors have been placed, the following intervention(s) will be applied during the stepped hypoxia plateau sequence:

- o Baseline blood samples will be obtained

Hypoxia breathing mixtures of O₂ / N₂ in air via a tight-fitting facemask.

- After measurements have been completed, the subject will be allowed to breathe room air.
- A study event flowchart of the stepped hypoxia plateau sequence is given below (figure 1).

- Recovery Period:

- The volunteer should remain in bed for one hour, and will be monitored using the remaining basic monitoring (see above) for another hour.
- The volunteer will be allowed to go home after the medical personnel determine that it is safe to do so. The volunteer should not drive a car by themselves, until 1 day after the study procedure. The volunteer is asked to refrain from strenuous exercise the first 48 hours after the study procedure.

- All blood samples will be immediately analyzed using satellite-lab blood gas analysis.

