6 STATISTICAL CONSIDERATIONS

6.1 Sample Size Calculation

The current study will be a repeated measures study with one group. The study is focused at assessing the agreement of $\text{SaO}_2/\text{SvO}_2$ readings with O3-derived rSO_2 readings during a stepped hypoxia plateau sequence protocol. A high level of correlation among repeated measures (0.9) is assumed.

The calculation(s) of the required sample size comply with formal requirements in the U.S. by the FDA, which require for NIRS validation studies the inclusion of at least 12 subjects[9].

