6.2 Statistical Plan

All analyses will be performed for pooled data from all sensors, as well as broken down per individual sensor. As the aim of the study is to investigate agreement of Masimo O3 regional oximeter-derived rSO_2 readings with the invasive blood gas derived gold standard(s), conventional method comparison statistics (i.e. bias, precision and repeatability) will be performed.

Primary Study Parameter(s): The data from this study will be analyzed using a mixed effects analysis with subject as random effects terms. By adding an additional factor identifying replicate data points, the repeatability of cerebral and somatic O3 rSO_2 values ($\Delta\text{rSO}_2(\text{O3}) - \Delta\text{rSO}_2(\text{Gold Standard})$) will be estimated and used to correct Limits of Agreement for repeated measures on the same subject. Bland Altman Plots will be created showing the calculated Limits of Agreement. These will be evaluated to check whether the variance of rSO_2 from the investigated devices and the invasive gold standard, is constant over the range of hypoxia studied.

Other Study Parameter(s): To evaluate the evolution of continuous hemodynamic variables (stroke volume, arterial blood pressure) during the study protocol, the Mann-Whitney test will be used. Categorical variables (gender, skin pigmentation as assessed by the Massey scale) will be analyzed with the Fisher's Exact test.

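### Section 6.2 names the Mann-Whitney test, which needs two independent samples, for within-subject change in stroke volume and arterial pressure

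*Combined protocol and SAP*

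**What the plan says.** Section 6.2, under 'Other Study Parameter(s)', states: "To evaluate the evolution of continuous hemodynamic variables (stroke volume, arterial blood pressure) during the study protocol, the Mann-Whitney test will be used". No other method is given for these variables.

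The design is set out elsewhere in the same document. Section 6.1 says "The current study will be a repeated measures study with one group" and adds "A high level of correlation among repeated measures (0.9) is assumed". Section 5.3 says "Each subject will undergo the following interventions in a standardized sequence", starting with room air and moving to hypoxia; the hypoxia levels are redacted. Section 5.4 provides an arterial catheter for "continuous monitoring of arterial blood pressure". Section 4.1 sets the target at 25 subjects.

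Section 6.2 also specifies a mixed effects analysis with subject as a random effect. It appears under 'Primary Study Parameter(s)' and goes on to rSO₂ repeatability and limits of agreement. It is not assigned to the hemodynamic variables.

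**The concern.** How a variable evolves over the protocol is a question about change within the same volunteers from phase to phase. Mann-Whitney compares two samples of different, independent subjects. It discards the pairing and computes its null variance as if the two sets of values were unrelated. It also compares only two conditions at a time, whereas the sequence is stepped.

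At stake is whether the reported p-values for hemodynamic change can be read at face value. If one value per subject per phase is used, a real moderate change in pressure or stroke volume could be reported as not significant. If many readings from the continuous arterial trace are entered as though independent, a chance difference could be reported as real. The visible text does not say which applies, so a reader could not tell the direction of the error.

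**Working it through.** **Inputs from the document.** One group with repeated measures (6.1); the same sequence for every subject (5.3); n = 25 (4.1); correlation 0.9 (6.1). The visible text gives no alpha, power, effect size or SD for the hemodynamic analysis, so there is no planned figure to reproduce.

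**Assumptions.** Two-sided 5%; normal data; two phases; shifts in units of the SD of a single value. The 0.9 is stated for the rSO₂ agreement design. Carrying it over to hemodynamics is an assumption, so 0.5 and 0.7 are shown as well.

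**Step 1: large-sample type I error, one value per subject per phase.** Positive correlation shrinks the true variance of the Mann-Whitney statistic by the factor 1 − ρ_S, where ρ_S = (6/π)·asin(ρ/2) for normal data. The test still uses the unshrunk variance, so its actual level is 2·[1 − Φ(1.96/√(1 − ρ_S))].

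- ρ = 0.5: ρ_S = 0.483; 1.96/√0.517 = 2.72; level 0.6%.
- ρ = 0.7: ρ_S = 0.683; 1.96/√0.317 = 3.48; level 0.05%.
- ρ = 0.9: ρ_S = 0.891; 1.96/√0.109 = 5.95 (before rounding); level below 0.001%.

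The level is 5% only at ρ = 0.

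**Step 2: simulation of the same case** (10,000 runs per cell, n = 25). Entries are rejection rates, Mann-Whitney / Wilcoxon signed-rank.

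| ρ | no shift | 0.3 SD | 0.5 SD | 0.8 SD |
|---|---|---|---|---|
| 0.5 | 0.7% / 4.5% | 9.5% / 28.7% | 34.9% / 64.0% | 83.3% / 96.3% |
| 0.7 | 0.1% / 4.8% | 5.8% / 43.7% | 33.4% / 85.9% | 88.7% / 99.8% |
| 0.9 | 0.0% / 4.6% | 1.8% / 88.0% | 30.1% / >99.9% | 96.2% / 100.0% |

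The no-shift column agrees with step 1. The loss of power is severe for small and moderate shifts. A 0.8 SD shift is usually found, though at ρ = 0.5 Mann-Whitney misses about 17% of such shifts against about 4% for signed-rank.

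**Step 3: several readings per subject per phase stacked as independent, no true shift.** Total variance is 1, split into subject / subject-by-phase / residual. The splits and the number of readings are assumptions. Entries are Mann-Whitney type I error.

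| Variance split | 1 reading | 4 readings | 8 readings |
|---|---|---|---|
| 0.5 / 0.4 / 0.1 | 0.6% | 14.2% | 28.9% |
| 0.7 / 0.2 / 0.1 | 0.1% | 5.4% | 16.3% |
| 0.5 / 0.2 / 0.3 | 0.7% | 6.6% | 16.6% |
| 0.8 / 0.1 / 0.1 | 0.0% | 1.2% | 5.9% |
| 0.9 / 0 / 0.1 | 0.0% | 0.0% | 0.0% |

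In an extreme split with no stable subject effect (0 / 0.9 / 0.1), a separate run with 5 readings gave 36%. A signed-rank test on subject means stays at 4.6% to 5.2% in every cell of the table.

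**The case against.** The strongest case on the other side is about weight. These are supplementary variables. The visible text attaches no hypothesis, success criterion or decision to them. The visible primary objective and endpoint concern rSO₂ agreement, and the early termination conditions in section 5.4 act on each individual's own readings, not on a group p-value. This stands, and it limits the point to the analysis under 'Other Study Parameter(s)'.

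A second argument is redaction. The hypoxia steps, parts of the endpoint section and the flowchart are not visible, and they may define the time points and the readings per step. This stands for the number of readings, which should therefore be read as a question to settle and not as a proven omission. It does not rescue the choice of test. The sentence in 6.2 is complete, and no number of steps makes repeated values from the same volunteers independent.

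A third argument is that the sizes rest on assumptions: a 5% level the document does not state, a correlation borrowed from the rSO₂ context, and variance splits chosen for illustration. This is fair. Nothing in the plan says readings will be stacked, so step 3 shows only that the direction can reverse. The one-value-per-subject result carries the weight, and it holds across the whole correlation range shown.

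**Conclusion.** The concern holds. An independent-samples test is named for a one-group, repeated-measures comparison, and the visible plan offers no paired alternative for these variables.

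With one value per subject per phase and positive correlation, the test is strongly conservative: type I error is 0.7% or less for correlations of 0.5 to 0.9, and power for a 0.5 SD shift is roughly 30% to 35% where a paired rank test has 64% to more than 99%. If readings were stacked, the type I error could instead exceed 5%, by an amount that depends on variance components the documents do not give. These sizes assume n = 25, two phases, normal data and a two-sided 5% level.

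The primary agreement analysis and subject safety do not depend on this test. The correction should be made, but it does not threaten the study's main result.

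**What to change.** Replace the Mann-Whitney sentence in section 6.2 with a linear mixed model for each hemodynamic variable: hypoxia step as a fixed effect and subject as a random effect, in line with the primary analysis, reporting change from baseline with a 95% confidence interval. State how many readings per subject per step enter. Either reduce them to one summary value, or keep them all and add a subject-by-step random effect.

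If a rank method is preferred, take one summary value per subject per step, use the Friedman test across steps, and follow it with Wilcoxon signed-rank tests against baseline under a stated multiplicity rule such as Holm. The rule is needed because several steps share one baseline. With 2 to 5 steps (the actual number is redacted), unadjusted signed-rank tests give at least one false positive in 9% to 18% of simulated studies; with Holm it is 3.6% to 4.6% (20,000 runs, correlations 0.5 and 0.9).

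The cost is one or two sentences in the statistical plan. No extra data or change in study procedures is needed.

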7 BENEFITS / RISK ANALYSIS

Benefits: There are no benefits to enrolled subjects. Information gained from this research study may help develop new technologies that may be beneficial for future patients.

Non-Invasive Measurement Risks: The risk from non-invasive devices is minimal since the measurements are non-invasive and derived with optical technology.

Sensor Risks: As with all optical sensors, the investigational device has the theoretical risk of thermal burn. The design includes safeguards, and this risk is believed to be very low. Pressure damage may occur to the tissue if the sensor is placed too tightly. Sensors will be attached with adhesive, and those on the forehead may be secured by a supplemental headband. This risk is believed to be low. Optical exposure is minimized by procedure and low power. This risk is believed to be low.

Lidocaine Risks: Administration of lidocaine injection, as a local anesthetic to facilitate placement [REDACTED] [REDACTED] [REDACTED] may be discomforting and can feel like a slight pinch along with warm/burning sensation. Other anticipated adverse events that may occur include but are not limited to: flushing or redness of the skin, itching skin, small red or purple spots on the skin, unusually warm skin, bruising, bleeding at the application sites, and swelling. These adverse events are expected to be temporary. Although not common, it is also possible to have an allergic reaction to injectable lidocaine. Subjects should not take part in this study if they are allergic to lidocaine injection or other types of numbing medicine, or if they have a heart rhythm disorder such as Wolff-Parkinson-White Syndrome or Stokes-Adams Syndrome. Subjects are instructed to tell the study staff right away if they experience hives; difficulty breathing; or swelling of the face, lips, tongue, or throat.

[REDACTED] **Venous Catheter Placement Risks:** Placement of a venous catheter over a sheath will be performed by a certified and qualified interventional radiologist. Placement of a venous catheter via a [REDACTED] venous sheath is, when placed using ultrasound-guidance, regarded safe[18]. Typical – but rare – complications may include local hematoma and hemorrhage. The catheter will be a [REDACTED] for which the correctness of its positioning will be verified by [REDACTED] x-ray. The (carcinogenic) risk of a single x-ray is negligible.

Radial Artery Line Placement Risks: Placement of the arterial line will be done by a certified and qualified anesthesiologist. These cannulas are used routinely in standard perioperative anesthetic care. Arterial catheters have been found to be relatively safe with a low incidence of serious complications[13]. Typical complications include temporary radial artery occlusion and hematoma. (Very) rare complications (less than 1% of procedures) include localized catheter site infection, hemorrhage, sepsis, permanent ischemic damage and pseudo-aneurysm formation. All these risks are very rare in volunteer populations, especially when used for short-term monitoring [17].

Stepped Hypoxia Plateau Sequence Protocol Risks: The risks of the brief exposures to hypoxia include feeling short of breath, headache, dysrhythmia, and dizziness. Brief loss of consciousness may occur, but is not expected at the levels of oxygen targeted for these tests given the magnitude of comparable studies, in which none of the events mentioned previously, occurred.[8,9,14-16] The methods comply with FDA and ISO standards [9,11].

Mitigating Risks: This study employs methods that are similar to standardized protocols as set by the FDA and ISO standards for testing pulse oximetry devices under controlled hypoxia[11]. For this study, only capacitated healthy adult volunteers will be included. During the study, the volunteers will be observed closely by at least one certified anesthesiologist, and at least one qualified nurse. Placement of the arterial line will be done by a certified and qualified anesthesiologist. These cannulas are used routinely in standard perioperative anesthetic care.

In a similar healthy volunteer study, we have previously performed controlled hypoxia procedure(s) without any unwanted sequelae[14]. During the study, the volunteer will remain under the care of the research team which includes at least a certified nurse or doctor after the study is concluded. If, after 2 hours in the recovery phase of the study, the volunteer meets the UMCG standard day care discharge criteria he/she can be discharged home. If the volunteer does not meet the discharge criteria he/she will be observed until deemed fit for discharge.

8 SAFETY AND ADVERSE EVENTS

8.1 Definitions

The definitions for adverse event, adverse device effect, serious adverse event, serious adverse device effect, and unanticipated adverse device effect are provided below (ISO 14155:2011, 21 CFR 812.3(s)).

- **Adverse Event (AE):** an adverse event is any untoward medical occurrence in a subject which need not be related to the device under investigation.
- **Adverse Device Effect (ADE):** an adverse device effect is any untoward or unintended response to a medical device which may result from insufficiencies in the instructions for use or deployment of the device, or from use error.
- **Serious Adverse Event (SAE):** a serious adverse event is an adverse event that results in death, inpatient hospitalization, severe or permanent disability, a life threatening illness or injury, fetal distress, fetal death, a congenital abnormality, a birth defect, or medical or surgical intervention to prevent permanent impairment to body or structure.
- **Serious Adverse Device Effect (SADE):** a serious adverse device effect is an adverse device effect that results in death, inpatient hospitalization, severe or permanent disability or is life threatening.
- **Unanticipated Adverse Device Effect (UADE):** any serious adverse effect on health or safety or any life threatening problem or death cause by or associated with, a device, if the effect, problem, or death was not previously identified in nature, severity or degree of incidence in the investigational plan, or application (including a supplementary plan or application) or any other unanticipated serious problem associated with a device that related to the rights, safety or welfare of subjects.

Refer to the Risk/Benefit section for details on anticipated adverse device effects and potential risks associated with the study procedures.

8.2 Temporary Halt for Reasons of Subject Safety

The sponsor will suspend the study if there is sufficient ground that continuation of the study will jeopardize subject health or safety. The sponsor will notify the accredited IRB/ethics committee without undue delay of a temporary halt including the reason for such an action. The study will be suspended pending a further positive decision by the accredited IRB/ethics committee. The investigator will take care that all subjects are kept informed.

8.3 Anticipated Adverse Events

8.3.1 Device-Related Adverse Events

- Sensors may cause thermal burn, pressure damage, mild allergic reaction, discomfort, redness, or skin irritation.

8.3.2 Procedure-Related Adverse Events

- Refer to the Benefits/Risk Analysis Section.

8.4 Adverse Event Reporting

The PI must follow the guidelines below and promptly report adverse events to the Sponsor through the CRF and Adverse Event Report Form, and must follow their IRB/ethics committee policy for safety event reporting:

- All Adverse Events, both Anticipated and Unanticipated and serious and non-serious, for the duration of the subject's enrollment in the study until subject completion of the study, shall be reported to the Sponsor and/or IRB/ethics committee.
- SAEs must be reported to the Sponsor within 48 hours. The sponsor shall report without delay any serious adverse event that has a causal relationship with the investigational device, the comparator or the investigation procedure or where such causal relationship is reasonably possible. The sponsor shall also report any device deficiency that might have led to a serious adverse event if appropriate action had not been taken, intervention had not occurred, or circumstances had been less fortunate. All other Adverse Events should be reported to the Sponsor within 5 business days. The sponsor will report the SAEs through the web portal *ToetsingOnline* to the accredited IRB/ethics committee that approved the protocol, within 7 days of first knowledge for SAEs that result in death or are life threatening followed by a period of maximum of 8 days to complete the initial preliminary report. All other SAEs will be reported within a period of maximum 15 days after the sponsor has first knowledge of the serious adverse events. SAEs will be reported to the Member State within 48 hours of awareness by the Sponsor. New information in relation to an already reported event will also be reported to the Member State within 48 hours.
- All Unanticipated Adverse Device Effects (UADEs), for the duration of the subject's enrollment in the study until subject completion of the study, shall be reported to the Sponsor and/or IRB/ethics committee. The investigator shall submit to the sponsor and to the reviewing IRB a report of any UADE occurring during an investigation as soon as possible, but in no event later than 10 working days after the investigator first learns of the effect. The Sponsor will evaluate the UADE to determine if it presents an unreasonable risk to study subjects. If the Sponsor determines there is an unreasonable risk to subjects, the Sponsor will notify the FDA, IRB, and investigator within 10 working days after the Sponsor first received the notice of the UADE.

